INCLUSION CRITERIA	
 - ≥18 years - Anticipated ICU stay ≥ 48 hours - Admission to ICU ≤ 72 hours before screening - Severe vitamin D deficiency (≤12 ng/ml or undetectable)
EXCLUSION CRITERIA	
 - Severe gastrointestinal dysfunction (> 400 ml residual volume)/unable to take study medication - DNR order/imminent death - hypercalcemia - known nephrolithiasis, active tuberculosis or sarcoidosis (within the last 12 months) - pregnancy/lactation - not deemed appropriate by study team/physician - hypersensitivity to drug or excipient
AIM OF THE TRIAL	To test if high-dose vitamin D3 is beneficial for the clinical outcome of adult critically ill adult patients with severe vitamin D deficiency
PRIMARY OUTCOME	28-day mortality
SECONDARY/SAFETY OUTCOMES	90-day mortality 1-year mortality ICU and hospital mortality Hospital and ICU length of stay SOFA Score at day 5 (48 hours tolerance) and number of organ failures (> 2 SOFA points in each of the 6 categories) Katz Activities of Daily Life (ADL) at day 90 Self - reported infections requiring antibiotics until day 90

	
Hospital and ICU readmission until day 90
 
Discharge disposition
 
Microbiome analysis day 0 and day 5 (optional, for Medical University Graz centers only)
 
Laboratory:25OHD and 1,25OH2D at day 1 and 5 (optional, for Medical University Graz centers only)
 
Safety outcomes:
 
Hypercalcemia on day 5 (48 hours tolerance)
 
Self reported falls, fractures until day 90
 
New episodes of kidney stones

FOLLOW UP PROCEDURE	
by telephone, 3 months,
 
by telephone, 12 months (mortality only)

RANDOMIZATION	
randomizer.at
 
stratification by ICU and gender

ETHICS COMMITTEE INFORMED CONSENT	
Austria: Deferred/surrogate informed consent (IC)
 
Germany: urgent approval of one legal substitute by court, surrogate IC by legal substitute, deferred IC
 
Switzerland: Deferred IC, relatives and unrelated physician

ESTIMATED RECRUITMENT RATES	
20-100 per center and year

DATA SAFETY MONITORING BOARD	
[name], Geneva
 
[name], Zurich
 
[name], Vienna

TIMELINE	
Submitted to ESICM Clinical Trials Group 12/2015
 
Submitted to Ethical Committee Graz Q3/2016
 
Submitted to Ministry of Health Q4/2016
 
Funding sources (KLIF) Q3 /2017
 
Recruitment Start Run-In-Phase Q4/2017
 
Rollout 2018-2021

TABLE OF CONTENT

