 - loading dose of 540,000 IU (dissolved in 37.5 ml of medium chain triglycerides - MCT) followed by 4000 IU daily (10 drops) for the entire active study period (90 days)
- Placebo: identical regime – loading dose of 37.5 ml MCT followed by 10 drops daily

This study uses a group sequential design, with one interim analysis when 50% of the planned enrolled patients in each arm (N=600 per arm) have completed their day 28 assessment by the independent data safety monitoring board. The enrollment of patients will continue while the interim analyses is performed.

EARLIEST START DATE

Q2 2017

RECRUITMENT PHASE

Anticipated 2-3 years based on estimated recruitment rates of 20-100 per center and year

END OF STUDY

The end of the study will be reached either at the interim analysis if the data safety monitoring board decides to stop the study prematurely. Otherwise, the study ends when 2400 patients have been included and completed visit 4 (day 90).

COENROLLMENT

Coenrollment may be allowed after careful review of the principal investigators and in case of unlikely biological interference between the VITDALIZE study and another study. This would be the case e.g. for a study assessing transfusion of older versus newer blood products, or different mechanical ventilation strategies. Likely coenrollment will only be executed in the United Kingdom.

OUTCOMES**PRIMARY OUTCOME**

The primary outcome will be 28-day mortality (starting from day 0 when the study medication loading dose is given).

SECONDARY OUTCOMES

Efficacy outcomes

- 90-day mortality
- 1-year mortality
- ICU and hospital mortality
- Hospital and ICU length of stay (starting at day 0, ending at discharge from the trial site or day 90)
- SOFA day 5 (48 hours tolerance)
- Number of organ failures day 5 (0-6; > 2 SOFA points in each of the 6 categories)

20/40

VITDALIZE study protocol, 1.3, 24.01.2018

[figure not shown]
- Laboratory: 25(OH)D and 1,25(OH)2D levels at day 5 (48 hours tolerance)
- Katz Activities of Daily Life (56) at day 90
- Self – reported infections requiring antibiotics until day 90
- Hospital and ICU readmission until day 90
- discharge disposition (home, rehabilitation, other hospital)

Safety outcomes

- Hypercalcemia at day 5 (48 hours tolerance)/during ICU stay
- Self-reported falls, fractures until day 90
- New episodes of kidney stones

PREDEFINED SUBGROUPS

- Kidney function (CKD 4 or lower vs. higher at inclusion)
- Sepsis (admission diagnosis) vs. non sepsis

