The labelling, filling of placebo bottles and distribution of the study medication to the study centers will be performed at a certified pharmacy (Graz or Salzburg).

Concomitant interventions

Routine low-dose vitamin D supplementation (≤ 800 IU/day) is allowed during the study period and will be documented.

Adherence assessment

At visit 4 (Day 90), compliance will be assessed using the percentage of actually taken doses compared to the prescribed doses (self reported or reported by the caregivers).

Active vitamin D metabolites

Although in the future it will be interesting and necessary to assess the potential need for additional active vitamin D in critical illness, and specifically acute/chronic kidney failure, we choose not to do so in this trial because of simplicity and costs.

STEERING COMMITTEE

The steering committee consists of the PI and the co-investigators.

VISIT PLAN / STUDY PROCEDURES

SCHEDULE OF EVALUATIONS

ASSESSMENT	Screening VISIT -1	Enrollment Baseline data, loading dose VISIT 1	VISIT 2	VISIT 3	VISIT 4	VISIT 5
	Day -9 to Day 0	Day 0	Day 5	Day 28	Day 90	Month 12
Time window (days)			±2		±14	±30
25(OH)D	X					
inclusion/exclusion criteria	X	X				
signed informed consent if possible, otherwise deferred/surrogate	X	X				
randomisation		X				
demographics		X				
SAPS III		X				
TISS 28		X				
Charlson comorbidity index		X				
Stool sample (microbiome, subgroup) (optional, for Medical University Graz centers only)		X	X			
SAFETY EVALUATION						
Serum calcium	X	X	X	(X)		
Falls					X	
Fractures					X	
New episodes of nephrolithiasis					X	
Intervention						
Loading dose 540,000 IU		X				
Daily dose 4,000 IU			X	X	X	
Outcome variables						
Mortality			X	X	X	X
SOFA		X	X			
qSOFA		X				
Number of organ failures		X	X			
Infections requiring antibiotics					X	
Hospital and ICU readmission					X	

Discharge disposition					X	
Katz Activity of Daily Living		X			X	
25(OH)D (optional, for Medical University Graz centers only)		X	X			
1,25(OH)2D (optional, for Medical University Graz centers only)		X	X			

VISIT -1 (SCREENING)

25(OH)D screening is performed within clinical routine of the trial sites. Screening should be performed within the first 72 hours after ICU admission, and 25(OH)D routine testing should be available within 72 hours. After a patient has been identified to be eligible for the trial, the study medication should be given within 72 hours (max. 9 days).

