At day 5, extensive clinical and laboratory data will be collected, including several measures of severeness of morbidity. It is likely that the majority of all patients will still be hospitalized. In the unlikely case a patient will be discharged before day 5 the data will be collected at discharge (day 3 or day 4).

VISIT 3 (DAY 28)

At visit 3, the primary endpoint (28-day mortality) will be assessed. For Austria, this information may be collected from Statistik Austria. Otherwise, this information will be obtained by the research team including nurses through the patient data management system and/or telephone.

VISIT 4 (Day 90 ± 14d)

A follow up visit will be done by telephone 90 days after study inclusion by each study center: 1) family physician and/or 2) patient and/or 3) hospital). This visit will include important safety evaluations and secondary outcomes. This is also the end of the active intervention.

VISIT 5 (1 year ± 1 month)

A final follow up visit (with results reported separately) will be done by telephone after 1 year. For Austria, Statistik Austria will be contacted first.

COMPLETION

The database lock will take place after the 90-day follow up of the last patient has been completed, all queries have been sufficiently well addressed and implemented in the database (applicable for the interim and the final analysis).

UNBLINDING FOR INTERIM AND FINAL ANALYSIS

For the formal planned interim analysis the DSMB statistician will get the unblinding list from the independent statistician responsible for the randomization procedure.

For the final analysis the unblinding list will be given to the study statisticians after database lock.

SAFETY ASSESSEMENTS

SAFETY MONITORING (SERUM CALCIUM, RENAL FUNCTION, FALLS AND FRACTURES)

Because of extremely high event rate in ICU patients and the well known risk profile of vitamin D3, safety monitoring will be restricted to known vitamin D-related adverse events.

Calcium and creatinine will be monitored regularly for routine purposes during ICU stay and recorded in the eCRF. Patients will be asked for new episodes of nephrolithiasis, falls and fractures at the 90-day-follow up telephone visit.

ADVERSE EVENT REPORTING

Only potential study drug-related adverse events (hypercalcemia, new episodes of nephrolithiasis, falls, and fractures) will be monitored and recorded up to 90 days.

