At day 90, Katz Activities of Daily Life Score, infections requiring antibiotics and hospital and ICU readmission will be assessed. The Self – reported infections requiring antibiotics and hospital and ICU readmission will be categorized as yes/no. Additionally, the number of infection episodes, number of antibiotics and -discharge disposition (home, rehabilitation, other hospital) will be presented. Comparison between groups will be performed using non-parametric tests and Chi-square tests.

Stool samples

In a subgroup, stool samples will be collected for microbiome analysis on day 0 and day 5. Stool samples are stored at -80°C. DNA extraction from stool samples will be performed by mechanical lysis with a MagnaLyser Instrument (Roche Diagnostics, Mannheim, Germany) and subsequent total bacterial genomic DNA isolation with the MagNA Pure LC DNA Isolation Kit III (bacteria, fungi) in a MagNA Pure LC 2.0 Instrument (Roche Diagnostics) according to the manufacturer's instructions. For amplification of bacterial 16S rRNA the template-specific sequence AGAGTTTGATCCTGGCTCAG and CTGCTGCCTYCCGTA, targeting the hypervariable region V1-V2 of the 16S rRNA gene, are used. PCR reactions for each sample are performed in triplicates. Subsequently the amplicons are purified according to standard procedures, quantified, pooled and sequenced with the MiSeq Reagent Kits v3 (600 cycles, Illumina, Eindhoven, Netherlands) according to manufacturer's instructions with 20% PhiX (Illumina). The generated FASTQ files are used for microbiota analysis. Raw reads from Illumina MiSeq are pre-processed and filtered using MOTHUR v.1.31. Reads are de-noised using PyroNoise and chimera-filtered with UCHIME. Pyrosequencing errors are reduced with pre.cluster and non-bacterial sequences were also excluded. High quality reads are aligned to the SILVA database and taxonomy was assigned by MOTHUR's implementation of the ribosomal database project (RDP)-classifier followed by binning into phylotypes based on taxonomy. The shared file is then converted into a biom table and passed on to QIIME's (v.1.9.1) core_diversity.py command using non-phylogenetic parameters.

Analysis of safety outcomes

The safety outcomes, (hypercalcemia on day 5, new kidney stones, self-reported falls, and fractures until day 90) will be analysed as binary variables and compared with Chi-square tests.

Subgroup analysis

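### The outcome list counts hypercalcaemia at day 5 or during the ICU stay, but the synopsis and the safety analysis use day 5 only

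*Protocol*

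**What the plan says.** The protocol describes the observation period for hypercalcaemia in four places.

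- **Synopsis, safety outcomes:** "Hypercalcemia on day 5 (48 hours tolerance"). The ICU stay is not mentioned.
- **Outcomes, Safety outcomes:** "Hypercalcemia at day 5 (48 hours tolerance)/during ICU stay".
- **Adverse event reporting** sets a longer recording period: "Only potential study drug-related adverse events (hypercalcemia, new episodes of nephrolithiasis, falls, and fractures) will be monitored and recorded up to 90 days".
- **Data analysis, Analysis of safety outcomes** fixes what is compared: "The safety outcomes, (hypercalcemia on day 5, new kidney stones, self-reported falls, and fractures until day 90) will be analysed as binary variables". The section then specifies chi-square tests.

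On data collection, the Safety monitoring section states: "Calcium and creatinine will be monitored regularly for routine purposes during ICU stay and recorded in the eCRF". The Schedule of Evaluations has serum calcium at screening, day 0 and day 5. A further entry in brackets appears to belong to day 28.

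The regimen is "loading dose of 540,000 IU (dissolved in 37.5 ml of medium chain triglycerides - MCT) followed by 4000 IU daily", the daily doses running "for the entire active study period (90 days").

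**The concern.** One safety outcome has a wider definition in the outcome list than in the section that says how it will be analysed. The analysis section does not leave the time point open. It fixes the narrower one.

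Take a patient with a normal day-5 calcium who becomes hypercalcaemic in the ICU on day 10. Under the outcome list this patient has the event. Under the analysis section the patient counts as having none. That stays true if the episode leads to withdrawal or unblinding, for both of which the protocol uses severe hypercalcaemia as its example. An event serious enough to break the blind could then be absent from the arm comparison, although the calcium value behind it is in the eCRF.

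The two sections could therefore yield different hypercalcaemia rates from the same data, and the choice between them should not be left until the results are known.

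**Working it through.** This is mainly a comparison of text. Arithmetic serves only to place day 5 within the treatment course.

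**Step 1. Observation period by section**

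| Protocol section | Period for hypercalcaemia |
|---|---|
| Synopsis | Day 5, 48 hours tolerance |
| Safety outcomes | Day 5, 48 hours tolerance, or during ICU stay |
| Adverse event reporting | Recorded up to day 90 |
| Analysis of safety outcomes | Day 5 |

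The ICU stay is in the outcome definition and missing from the analysis. No section describes a comparison of the arms on hypercalcaemia over the ICU stay or on later reported events.

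**Step 2. Are the data for the wider definition collected?** For the ICU stay, yes: routine calcium goes into the eCRF. For the time after the ICU, only in part. The bracketed entry is the only scheduled calcium after day 5. Day 90 is a telephone visit that asks about kidney stones, falls and fractures, with no calcium measurement.

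**Step 3. Reproduce the stated total dose.** Inputs: loading dose 540,000 IU, 4,000 IU daily, 90 days.

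540,000 + 90 × 4,000 = 900,000 IU, which agrees with the protocol.

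**Step 4. Place the day-5 window.** Assumption: daily doses start on day 1. Dose given by day d = 540,000 + 4,000 × d.

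| Day | Dose given (IU) | Share of 900,000 | Daily-dosing days left |
|---|---|---|---|
| 3 (window opens) | 552,000 | 61% | 87 of 90 |
| 5 | 560,000 | 62% | 85 of 90 (94%) |
| 7 (window closes) | 568,000 | 63% | 83 of 90 (92%) |

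At day 5, 340,000 IU (38%) is still to be given. The result hardly changes across the window.

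**Step 5. Is there an outcome cut-off?** The exclusion criteria give limits at screening: above 2.65 mmol/l total and/or above 1.35 mmol/l ionised calcium. The section on randomization and blinding gives 3.5 mmol/L as an example of severe hypercalcaemia that may lead to unblinding. Neither is stated to define the outcome.

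**The case against.** The best defence is that day 5 is a reasoned choice. It falls soon after the bolus, which alone is 60% of the total dose (540,000 / 900,000), and it is the only scheduled post-dose calcium without brackets. The protocol's background presents the daily dose as the recognised upper intake limit, and cites a review linking hypercalcaemia only to prolonged intakes well above it. A fixed day also avoids a real difficulty: with a count over the whole ICU stay, an arm that survives longer or stays longer gets more measurements and more chances of a positive value. All of this stands. It supports keeping day 5, but does not explain why the outcome list adds the ICU stay and the analysis drops it.

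A second defence is that General aspects and Missing data handling promise that all collected or available data will be used, and that the SAP prevails where it differs. So a reader who infers that later calcium values will be ignored altogether goes too far; they may well be summarised. But a general promise names no endpoint and does not override the specific one in the analysis section.

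Three further inferences are not supported:

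- **That early discharge removes patients from the analysis.** The Visit 2 section has data collected at discharge on day 3 or 4. Only death or discharge before day 3 would clearly leave no value.
- **That the eCRF already supports a full day-90 calcium endpoint.** Step 2 shows that it does not.
- **That hypercalcaemia is ranked as the main harm.** The protocol lists it first among the drug-related events but ranks none of them.

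**Conclusion.** The protocol contradicts itself on the scope of this outcome, and the analysis as written leaves out ICU hypercalcaemia after the day-5 window, which the outcome list includes and the eCRF can supply.

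In treatment terms, day 5 comes after 62% of the total dose and before 85 of the 90 daily-dosing days, assuming daily doses from day 1. Both figures are needed. A reader who looks only at the remaining days might infer that the analysis misses most of the exposure; by dose that is not so. With no hypercalcaemia rate in the protocol, nothing shows what share of events day 5 would miss.

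The conclusion rests on the protocol alone. The SAP was not available and may already settle the endpoint, but the protocol sections would still need to agree. The change should be made, since it concerns a named safety outcome and uses data already collected.

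**What to change.** 1. Reconcile the Synopsis, Safety outcomes, Adverse event reporting and Analysis of safety outcomes, so that they give one definition and one observation period for each hypercalcaemia analysis.
2. Compare the arms on any hypercalcaemia at day 5 or during the ICU stay, using the recorded calcium values. Keep day 5 (48 hours tolerance) as the fixed-time comparison.
3. State the calcium cut-off that defines the outcome. The protocol now gives limits for exclusion and an example for unblinding, but none for the outcome.
4. Tabulate hypercalcaemia adverse events to day 90 by arm in a separate table, labelled as reported events because calcium is not systematically measured after the ICU.
5. Show the number of calcium measurements and the time at risk by arm beside the ICU-stay result.

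**Cost.** Text changes in the protocol and SAP and some extra tables. No new sampling is needed, provided the eCRF holds dated individual ICU values, which should be confirmed. The small downside is that the ICU-stay endpoint depends on length of stay and survival. Item 5 makes that visible, and the day-5 comparison gives a result less affected by it.

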If the major inclusion criterion of severe vitamin D deficiency is met, the other inclusion and exclusion criteria are evaluated by the local investigator/s at Visit 1. Informed consent will be ascertained whenever possible.

BASELINE ASSESSMENTS

- Age
- Sex
- ICU admission diagnosis
- ICU type
- Charlson comorbidity index
- SAPS III
- TISS 28
- 25(OH)D routine testing
- qSOFA
- Katz Activities of daily life

At baseline, data on demographic and clinical characteristics of the patients are obtained. At Centers of Medical University Graz it is planned to take a blood sample before the loading dose on day 0 and day 5 to ascertain biochemical response. The samples will be stored frozen at -70 C until batch analysis. In this subgroup (Medical University Graz), also stool samples will be collected for microbiome analysis on day 0 and day 5 . Stool samples are stored at -80°C

The Charlson comorbidity index, SAPS III and TISS 28 will be determined to be able to adjust for severity of illness and preexisting comorbidities.

RANDOMIZATION AND BLINDING

Patients will be randomly assigned to either placebo or vitamin D3 in a 1:1 ratio, using the web-based randomization service "Randomizer for Clinical Trials" developed at the Institute for Medical Informatics, Statistics and Documentation, Medical University of Graz. Patients will be stratified according to trial site (ICU) and gender. An independent statistician will set up the study in the Randomizer.

The following method will be used to maintain the blind: the randomization list from the randomizer.at will be kept strictly confidential and no routine vitamin D testing is done after study inclusion. The independent statistician and unblinded pharmacist will keep treatment allocation information confidential until database lock.

In case of safety concerns (eg. severe hypercalcemia > 3.5 mmol/L), participants of the study may be unblinded by the local investigator at each participating site and/or the coordinating center. This will be done and documented with the Randomizer.

VISIT 1

Study medication

The day of the study medication loading dose is day 0. This is also the start for the calculation of the time dependent outcome data.

VISIT 2 (DAY 5 ±2)

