All clinical and safety data collected in the study will be analysed with SAS v9.4 procedures in a Windows XP environment. Data will be presented as summary tables and, where appropriate, as plots. Continuous data will be described by means, standard deviations, medians and upper and lower quartiles unless otherwise stated. The number of observations and minimum and maximum values are also included. All descriptive summaries will be displayed to one more decimal place than actually measured. Categorical data will be summarized using frequencies and percentages.

Demographic and Baseline Characteristics

In a summary of demographic, baseline and diagnostic characteristics (age, weight, height, sex, SAPS III, Charlson comorbidity index, qSOFA - criteria, laboratory parameters,...) a comparison of the treatment groups will take place. To this end, appropriate descriptive and inferential statistics will be applied. Relevant medical history will be also displayed using summary statistics according to the two treatment groups.

Analysis of primary outcome

The primary outcome will be 28-day mortality defined as time from application of the study medication loading dose (day 0) to day 28 or death. Kaplan Meier estimates of survival curves in each treatment arm will be displayed. Group comparison will be made using a two-sided log rank test. Additionally, a hazard ratio with a 95% confidence interval will be computed from an univariate Cox-proportional hazards regression. Furthermore sensitivity analyses using multivariable Cox-proportional hazards regression will be performed adjusting for important clinical parameters. Details will be defined in the SAP.

Analysis of secondary outcomes

ICU, hospital mortality, 90-day mortality and 1-year mortality will be analysed as the primary outcome. ICU and hospital length of stay are defined as time between application of the study medication (day 0) and discharge at the primary ICU/hospital; readmissions and stays

at other hospitals will not be added, date and hour will be recorded, in case of a missing hour, the time 12am will be used.

At day 5 the SOFA Score is recorded. Organ failures (> 2 SOFA points in each of the 6 categories) will be reported in total and for each organ system separately. To compare the laboratory parameters 25(OH)D and 1,25(OH)₂D levels ANCOVA will be used.

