Predefined subgroup analyses will be performed for all primary and secondary outcomes based on the following group definitions as exploratory analysis:

- Kidney function (CKD 4 or lower vs. higher at inclusion)
- Sepsis (admission diagnosis) vs. non sepsis defined by the 2016 criteria (suspected infection/qSOFA on day 0 – respiratory rate of 22/min or greater, altered mentation, or systolic blood pressure of 100 mm Hg or less (57))

MISSING DATA HANDLING

All available data will be used in the analyses and data summaries. There will be no imputation of any missing data.

SAMPLE SIZE AND INTERIM ANALYSIS

Sample size considerations

The sample size is based on the primary endpoint 28-day mortality. In the VITdAL-ICU study (2014), 28-day mortality rates of 36% (37/102) in the placebo group and 20% (20/98) in the Vitamin D Group were observed (51). In this multicenter study we assume 28-day mortality rates of 25% in the placebo group versus 20% in the vitamin D group. We assume that baseline (placebo) mortality will be lower in this study because in contrast to the previous VITdAL-ICU study, academic and non-academic smaller sites with patients with a lower severity of illness will participate.

Using a fixed sample size design and a two-sided log-rank test for equality of survival curves with a two-sided alpha level of 5%, a sample size of n=1093 per group will be needed to achieve a power of 80% (total sample size of 2186). The **Table** below shows the sample sizes when the assumptions about 28-day mortality rates are varied between 25% - 35% for the Placebo group and between 20% - 30% for the vitamin D group as well as when the observed 28-day mortality rates from Amrein et al (2014) are assumed.

Placebo 28-day mortality	25%		30%		Based on the VITdAL-ICU study
Alpha level	0.05	0.05	0.05	0.05	0.05
Placebo proportion alive (π_P) at time t	0.75	0.75	0.70	0.70	0.637
VitD proportion alive (π_{VitD}) at time t	0.80	0.81	0.8	0.75	0.796
Hazard ratio $\ln(\pi_{\text{VitD}})/\ln(\pi_P)$	0.78	0.73	0.63	0.81	0.51
Power (%)	80	90	80	80	80
n per group	1093	1002	296	1245	129
Total number of events required	486	434	143	679	68
N Total	2186	2004	592	2490	258

Table: Different sample size scenarios using a two-sided log rank test

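### The ban on imputation makes no exception for baseline covariates, so the adjusted Cox sensitivity models would drop patients whose survival is known

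*Protocol*

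**What the plan says.** Three places in the protocol bear on this.

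- **Missing data handling:** "All available data will be used in the analyses and data summaries. There will be no imputation of any missing data". The rule is stated outright. It is not limited to outcomes and not deferred to the SAP.
- **Analysis of primary outcome:** "a hazard ratio with a 95% confidence interval will be computed from an univariate Cox-proportional hazards regression", in addition to the log-rank test. As a check on this, "sensitivity analyses using multivariable Cox-proportional hazards regression will be performed adjusting for important clinical parameters". The covariates are not listed; the text adds "Details will be defined in the SAP".
- **Baseline assessments:** "The Charlson comorbidity index, SAPS III and TISS 28 will be determined to be able to adjust for severity of illness and preexisting comorbidities".

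The opening of Statistical considerations lets the SAP override the protocol where the two differ. The SAP is not at hand.

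**The concern.** A Cox model cannot use a record with a missing numeric covariate. If nothing may be imputed, the record is deleted, even when the date of death or survival to day 28 is known. The log-rank test and univariate Cox model need no covariates and keep that patient. With any score missing, the robustness check therefore runs on fewer patients than the result it checks, selected by how complete their baseline record is. A gap between the adjusted and unadjusted hazard ratios could then come partly from who was dropped.

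For outcomes the ban does little harm, since a patient without day-28 status can be censored. For baseline covariates it gives up information for no benefit. In a randomised trial, a baseline value filled in without reference to arm or outcome does not bias the treatment comparison.

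**Working it through.** **Inputs from the protocol (Sample size and interim analysis):** 28-day mortality 25% on placebo and 20% on vitamin D, mean 22.5%; hazard ratio 0.78; 2194 patients and 494 events for the group-sequential design; 2400 patients after drop-out; 1:1 allocation.

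**Input not in the protocol:** the share *m* of patients lacking at least one adjustment covariate. I assume 5%, 10% and 20%.

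**1. The plan's own figures reproduce.**
- HR = ln(0.80)/ln(0.75) = 0.7757 (stated 0.78).
- Events for 80% power in the fixed design, Schoenfeld: 4 × (1.960 + 0.842)² / (ln 0.7757)² ≈ 487 (stated 486).
- Freedman: 492 events; 492/0.225 = 2187 patients (stated 2186).
- Group-sequential: 2194 × 0.225 = 493.7 (stated 494).

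None of these is in dispute.

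**2. Loss of precision in the adjusted model.** With deletion unrelated to outcome, deaths kept = D × (1 − m). The standard error of the log hazard ratio is about 2/√deaths, so it grows by 1/√(1 − m), whatever D is. At 2400 patients, D = 2400 × 0.225 = 540.

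| m (assumed) | Patients dropped | Deaths kept | SE | SE increase | 95% CI around 0.776 |
|---|---|---|---|---|---|
| 0 | 0 | 540 | 0.0861 | – | 0.66 to 0.92 |
| 5% | 120 | 513 | 0.0883 | 2.6% | – |
| 10% | 240 | 486 | 0.0907 | 5.4% | 0.65 to 0.93 |
| 20% | 480 | 432 | 0.0962 | 11.8% | 0.64 to 0.94 |

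The intervals are exp(ln 0.7757 ± 1.96 × SE) and ignore any effect of adjustment itself. Losses add up across scores: three scores, each missing independently in 5% of patients, remove 1 − 0.95³ = 14.3%.

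**3. The mechanism in one simulated trial.** I took 2400 patients, one prognostic covariate and 10% of its values missing at random. The univariate Cox model used 2400 patients and 531 deaths. The multivariable model used 2168 patients and 469 deaths, so 62 deaths with known timing were lost. Hazard ratios were:
- univariate, all patients: 0.839
- univariate, complete cases: 0.827
- adjusted, complete cases: 0.805
- adjusted, all patients: 0.804

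Most of the gap between 0.839 and 0.805 is there without any deletion (0.839 against 0.804).

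**4. Bias.** Suppose 10% of deaths and 5% of survivors are lost equally in both arms.
- Placebo mortality among those kept: 0.225/(0.225 + 0.7125) = 0.240.
- Vitamin D: 0.180/(0.180 + 0.760) = 0.1915.
- HR = ln(0.8085)/ln(0.760) = 0.775, against 0.776 without loss.

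A visible shift needs loss that differs by arm. With 10% of deaths lost on vitamin D and 5% on placebo, and 5% of survivors lost in both, the HR becomes 0.739. Blinded recording of baseline scores makes that an unexpected case.

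**The case against.** **The adjusted models are left to the SAP.** The protocol lists no covariates and says only that the scores are collected so that adjustment is possible. If the SAP adjusted only for trial site and gender, the stratification factors, nothing would be lost. This stands as a limit on size. It does not make the rule sound, because the ban itself is fixed in the protocol without exception, and SAP precedence only shows where the repair can be made.

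**The two sentences of the rule do not conflict.** A reader might infer a contradiction with "All available data will be used in the analyses and data summaries". The natural reading is an available-case rule: analyse what was observed and substitute nothing. That reading is fair, so I do not claim a contradiction. Nor is deletion forced for categorical covariates, since a separate missing category substitutes no value; the problem is with numeric scores. The protocol itself departs from a strict ban when it sets a missing hour to 12am for length of stay, which suggests the wording is wider than intended.

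**Missing scores may be rare.** They are due at Visit 1 in the ICU, entered in an electronic case report form, monitored and queried before lock. This stands: no rate is given, and the loss could be nil.

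**A power shortfall might be inferred.** Converting the same losses to power on 494 deaths gives about 78%, 76% and 71%. The 80% target belongs to the log-rank test, which loses nobody. The sensitivity models carry no power target, so the comparison is not valid.

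**Comparability can be had without imputation.** Refitting the univariate model on the complete cases would put both hazard ratios on the same patients, and nothing forbids it. It would not recover the lost deaths. Even on identical patients the two hazard ratios differ, through non-collapsibility and chance covariate imbalance, so the fix removes one source of difference and not all.

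**Conclusion.** The point holds in a limited form. As written, "There will be no imputation of any missing data" would remove patients with known survival from the multivariable Cox sensitivity analyses whenever a numeric adjustment score is missing, so these would use fewer patients than the univariate Cox model. For an assumed 5%, 10% or 20% of patients affected, the standard error of the adjusted log hazard ratio rises by about 2.6%, 5.4% or 11.8%; with complete scores the cost is zero. This rests on the scores being in the model, which the protocol suggests but does not fix, and on the SAP not overriding the rule.

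The protocol does not support a reading in which the primary result is damaged or the adjusted hazard ratio materially biased. A reader might also extend the point to the ANCOVA of 25(OH)D and 1,25(OH)2D, but the protocol does not say that this analysis adjusts for a baseline value.

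Severity: minor. It is a cheap improvement.

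**What to change.** Limit the ban to outcome data, in the protocol or in the SAP, before the database lock for the interim analysis, so that the choice cannot look driven by results. Suggested wording:

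> Outcome data will not be imputed. In adjusted models, a missing numeric baseline covariate will be replaced by the overall mean together with a missing-value indicator, and a missing categorical covariate will form its own category, without reference to treatment arm or outcome. Every patient in the primary analysis set will be included in every adjusted model.

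The cost is this short passage and a few lines of code, with no new data and no more patients. The small downside is a few extra model parameters. Reporting the number of missing values per covariate would show how much the rule mattered.
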